6.2.12 Inexact Values

In the case where a variable is recorded as “> x”, “ \geq x”, “ $<$ x” or “ \leq x”, a value of x will be taken for analysis purposes.

6.2.13 Vital Signs

Body Mass Index (BMI) will be calculated as $[\text{weight in } ^\circ\text{KG}] \div ([\text{height in } ^\circ\text{CM}] \div 100)^2$.

6.2.14 Unscheduled Visits

Only scheduled post-baseline values will be tabulated. Post-baseline repeated, unscheduled and early termination assessments will not be included in tables, although these post-baseline assessments will be listed in the relevant appendices to the CSR.

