#### 9.3.1. Primary Endpoints

Safety analyses in this study will evaluate the safety profile of Engensis as compared with Placebo. The primary endpoints for safety are as follows:

- Incidence of TEAEs and TESAEs for Engensis compared to Placebo
- Incidence of injection site reactions for Engensis compared to Placebo
- Incidence of clinically significant laboratory values for Engensis compared to Placebo

No formal statistical testing will be conducted for the safety analyses. All Participants in the safety subset will be included in these analyses. Participants will be grouped by treatment received. All summaries will be derived based on available data. No imputation will be performed for missing values. All safety analyses will be made on the Safety Population.

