3 ENDPOINTS

3.1 Primary Endpoint

- Incidence of treatment-emergent adverse events (TEAEs) and treatment-emergent serious adverse events (TESAEs) for Engensis compared to Placebo
- Incidence of injection site reactions for Engensis compared to Placebo
- Incidence of clinically significant laboratory values for Engensis compared to Placebo

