6.2.2 Baseline

Baseline for safety parameters as well as for exploratory parameters is defined as the last non-missing value (either scheduled, unscheduled or repeat) before the participant receives first Study Injection.

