The following tables will be presented:

- Summary of TEAE (Table 14.3.1.1)

QMD Ref: Worldwide-TMP-ST-005-7.0 Effective: 12Aug2019	Governing QMD: Worldwide-SOP-ST-001
Confidentiality Statement	

This document is the property of Worldwide Clinical Trials Inc. and may not be duplicated, copied, altered or removed from company without prior approval from Worldwide Quality Assurance or in compliance with Worldwide Standard Operating Procedures.

Worldwide Clinical Trials Controlled Quality Management Document			
 WORLDWIDE CLINICAL TRIALS	Sponsor:	Helixmith Co., Ltd.	
	Protocol Number:	VMALS-002-2	
STATISTICAL ANALYSIS PLAN VERSION 3.0			

- TEAEs organized by SOC and PT (Table 14.3.1.2)
- TESAEs organized by SOC and PT (Table 14.3.1.3)
- TEAEs organized by SOC and PT and Maximum Severity (Table 14.3.1.4)
- TEAEs organized by SOC and PT and Maximum Relationship (Table 14.3.1.5)
- TESAEs organized by SOC and PT and Maximum Severity (Table 14.3.1.6)
- TESAEs organized by SOC and PT and Maximum Relationship (Table 14.3.1.7)
- Incidence Injection site reactions by SOC and PT (Table 14.3.1.8)
- Incidence of clinically significant laboratory values (Table 14.3.1.9)
- AESIs organized by SOC and (Table 14.3.1.10)
- TEAEs leading to study discontinuation by SOC and PT (Table 14.3.1.11)
- TESAEs leading to study discontinuation by SOC and PT (Table 14.3.1.12)
- TEAEs leading to study drug withdrawal by SOC and PT (Table 14.3.1.13)
- TESAEs leading to study drug withdrawal by SOC and PT (Table 14.3.1.14)
- TEAEs related to study medication by SOC and PT (Table 14.3.1.15)
- TESAEs related to study medication by SOC and PT (Table 14.3.1.16)

The following listings will be provided:

- All AEs (Listing 16.2.7.1)
- AESIs (Listing 16.2.7.2)
- TESAEs (Listing 16.2.7.3)
- Injection Site Reactions (Listing 16.2.7.4)
- TEAEs leading to study discontinuation (Listing 16.2.7.5)
- TEAEs related to study medication (Listing 16.2.7.6)
- TESAEs leading to death (Listing 16.2.7.7)

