Measured values of serum chemistry and hematology analyses and their changes from baseline, will be presented with descriptive statistics at each visit by treatment group (Tables 14.3.4.1 and 14.3.4.3). Incidence of clinically significant values and shift tables by the clinical significance based on laboratory assessments will be presented for each parameter (Tables 14.3.1.9, 14.3.4.2, 14.3.4.4). Percentages for each parameter will be based on the number of participants who have at least one measurement for at baseline and at corresponding post-baseline visit.

Result of urine pregnancy test is variable with two possible values: positive / negative. The test should be performed only for women with childbearing potential at Screening, Day 0 pre-dose and End of Study. Urinalysis will be presented only in a listing.

Results of serum chemistry, hematology and urine pregnancy tests will be listed (Listings 16.2.8.1 – 16.2.8.3).

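### SAP 6.2.14 keeps repeat, unscheduled and early-termination values out of all tables, with no exception for Table 14.3.1.9, the primary incidence of clinically significant laboratory values

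*SAP*

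**What the plan says.** SAP 3.1 lists "Incidence of clinically significant laboratory values for Engensis compared to Placebo" among the primary endpoints, as does Protocol 9.3.1. Table 14.3.1.9 reports it.

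SAP 6.2.14 sets a general rule for all tables: "Post-baseline repeated, unscheduled and early termination assessments will not be included in tables". Those values go to listings only.

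Two places in the SAP describe the table. Section 6.14.2, on laboratory data, says: "Incidence of clinically significant values and shift tables by the clinical significance based on laboratory assessments will be presented for each parameter", and cites Table 14.3.1.9 together with the two laboratory shift tables. Percentages there are "based on the number of participants who have at least one measurement for at baseline and at corresponding post-baseline visit". Section 6.14.1 also names it in its list of adverse event tables: "Incidence of clinically significant laboratory values (Table 14.3.1.9". Neither section brings back the values that 6.2.14 excludes.

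The protocol plans for such values. Footnote 8 of the Schedule of Activities puts chemistry and hematology at Screening and Days 60, 120 and 180/ET. Section 7.2 includes them in the ET visit, if that visit is possible. Section 10.2.5 foresees additional tests when an adverse event is followed up.

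**The concern.** Restricting by-visit means and shift tables to scheduled draws is ordinary practice and is not in question. An incidence endpoint asks something else: did a clinically significant value occur after treatment started? Leaving out collected values because of the visit at which they were drawn can remove events from that count but cannot add any.

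The ET draw matters more here than its name suggests, because the Day 60 and Day 120 samples are taken before dosing (Protocol 4.1.1). A participant who withdraws after one cycle's injections and before the next scheduled sample has only the ET draw as a protocol-specified laboratory sample after those injections. At stake is whether one primary table could show no event for such a participant while a TEAE table shows one.

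**Working it through.** The plan gives no figure to reproduce: N = 18 has no power calculation behind it, and Protocol 9.3.1 excludes formal safety testing. The check is therefore a reading of the text, followed by an illustration of size.

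**Step 1: does 6.2.14 reach the table?** Its wording is general and names no exception. Section 6.14.2 ties the incidence to laboratory assessments and to individual parameters, and gives a denominator of participants with measurements. That describes laboratory data rather than coded adverse events. Against this, the table is listed with the adverse event displays, and SAP Section 11 gives its shell as 14.3.1.3, the table of serious TEAEs. The shell column is weak evidence, since it also lists Table 14.6.9 as its own repeat. Laboratory assessments are the more natural source, but the SAP does not settle it.

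**Step 2: are ET draws lost?** The protocol heads its last column End of Study/ET, and SAP 6.14.2 tests at End of Study, so ET values might be mapped to that visit. But 6.2.14 names ET assessments as excluded, and SAP 6.2.8 treats discontinuation and End of Study as separate dates. If End of Study does include ET, only repeat and unscheduled values are lost.

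**Step 3: size with one affected participant.** Inputs: 12 Engensis and 6 Placebo (Protocol 5.3). Assumptions: everyone is treated; one participant in the arm has a clinically significant value only at an ET or extra draw; all others have all three scheduled draws and no such value.

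Counting once per participant:
- Engensis: 1/12 = 8.3% becomes 0/12, or 0/11 if withdrawal is before the Day 60 visit.
- Placebo: 1/6 = 16.7% becomes 0/6, or 0/5.

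Section 6.14.2 does not say whether the incidence is by visit or once per participant. If it is by visit, a withdrawal with the value seen only at ET gives:

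| Withdrawal | Engensis: Day 60, Day 120, End of Study | Placebo: Day 60, Day 120, End of Study |
|---|---|---|
| Before Day 60 | 0/11, 0/11, 0/11 | 0/5, 0/5, 0/5 |
| Day 60 to Day 120 | 0/12, 0/11, 0/11 | 0/6, 0/5, 0/5 |
| Day 120 to Day 180 | 0/12, 0/12, 0/11 | 0/6, 0/6, 0/5 |

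Each cell is correct for its visit, but the event appears in none.

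**Step 4: exposure with no tabulated sample after it.** Inputs from Protocol 4.1.1: 128 injections per dosing day, 0.25 mg each on Engensis, 192 mg in total. After both injection visits of a cycle: 2 × 128 = 256 injections; 256 × 0.25 mg = 64 mg; 64/192 = 33.3% of the planned dose. After one visit: 128 injections, 32 mg.

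**Step 5: how likely?** The documents give no rate. As an assumption only, let the ET rate p and the chance q that a terminator has a clinically significant value seen only at ET each range from 5% to 20%. The chance that at least one of 18 is affected is 1 − (1 − pq)^18. At p = q = 5% this is 1 − 0.9975^18 = 4.4%. At p = q = 20% it is 1 − 0.96^18 = 52.0%. The width of that range shows only that the number cannot be fixed in advance.

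**The case against.** The strongest reply is that the harm is conditional. If Table 14.3.1.9 is built from adverse event records, 6.2.14 does not touch it. In the SAP sentence, the reference to laboratory assessments could also be read as attaching only to the shift tables. This stands as a reason to state the source, but the parameter-based wording and measurement-based denominator make it the less natural reading.

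The signal should also survive elsewhere. Protocol 8.2.6 and 10.2.1 mean that a clinically significant value should normally be recorded as an adverse event, and so reach the TEAE tables. SAP 6.3 lists all data, and line listings for 18 participants can be read in full. A participant who stops only study drug may stay in for safety follow-up (Protocol 7.1), so those affected are study withdrawals and people with extra draws. In the earlier ALS study, 17 of 18 completed 9 months and one died (Protocol 2.2.6.1); that study was open label and single center, so it is only indicative. All of this stands, and it limits the weight of the point.

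A reader might infer three stronger things that the documents do not support:
- **That the SAP contradicts Protocol 9.3.1.** That section says "All Participants in the safety subset will be included in these analyses" and "All summaries will be derived based on available data. No imputation will be performed for missing values". The first sentence is most naturally about the analysis population. The second concerns missing values. Neither requires every participant in every laboratory denominator, or every unscheduled value in a table.
- **That the baseline rule makes 6.2.14 inconsistent.** SAP 6.2.2 takes "the last non-missing value (either scheduled, unscheduled or repeat) before the participant receives first Study Injection" as baseline. Choosing one pre-dose value and tabulating scheduled visits afterwards serve different purposes, so the difference is not an error.
- **That adverse event reporting loses the event.** Section 6.2.14 concerns assessments. The adverse event tables are not restricted by it.

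**Conclusion.** The point holds for one table and should be fixed before database lock. As written, a stated SAP rule can remove an observed event from a primary incidence table, on the reading that the table comes from laboratory assessments.

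One affected participant changes the displayed incidence by 8.3 percentage points on Engensis or 16.7 on Placebo. This assumes 12:6 treated, once-per-participant counting and no other event in that arm. With no affected participant the effect is zero. Because safety is purely descriptive, these counts are themselves the reported result. The defect is an incomplete primary table rather than a concealed safety signal. Confidence is medium, because the table's source and the meaning of End of Study remain open.

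**What to change.** Keep 6.2.14 as it stands, so that every other table still has a clear rule, and add one exception:

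> Table 14.3.1.9 counts all post-baseline values, including repeat, unscheduled and ET values.

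In 6.14.2 state:

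> Table 14.3.1.9 is built from laboratory assessments. For each parameter a participant counts once if any post-baseline value is clinically significant; the denominator is treated participants with at least one post-baseline value of that parameter. The count from scheduled plus ET draws only is shown alongside, with a footnote that extra draws give more chances to be counted.

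Do not take participants who were already clinically significant at baseline out of the count. The endpoint has no such restriction, Protocol 10.2.1 includes results that worsen from baseline, and the shift tables show baseline status. Also state whether End of Study includes ET, and correct the shell reference of 14.3.1.9 if it is wrong.

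The cost is a short SAP amendment and the programming of one table, possibly with a new shell. The values are already collected and listed, so no new data and no protocol amendment are needed. The downside is that the denominator will differ from the by-visit tables and that participants with extra draws have more chances to be counted. The parallel count and its footnote make that second effect visible.

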### 7.2. Participant Withdrawal/Discontinuation

Any Participant may voluntarily discontinue the study at any time without prejudice. The Investigator may discontinue a Participant from the study at any time if, in the Investigator's judgment, the Participant's health or safety would be compromised by remaining in the study.

Specific reasons for study discontinuation include the following:

- Participant decision
- Investigator's decision
- Adverse event
- Insufficient compliance with study requirements
- Lost to follow-up
- Other

The specific reasons for Participant discontinuation will be recorded.

The following assessments will be performed at an Early Termination (ET) Visit, if possible, for Participants who discontinue prior to the Day 180 Visit.

- Complete Physical examination
- Vital signs, weight
- 12-lead ECG
- Serum chemistry and hematology
- Urine pregnancy test
- SVC
- Concomitant medications
- Muscle strength by HHD
- ATLIS (where available)
- ALSFRS-R
- ALSAQ-40
- PGIC and CGIC
- Injection site reaction assessment if discontinued prior to Day 144
- Treatment-emergent adverse events

---

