6.1.2 ITT Population

The Intent to Treat (ITT) Population consists of all randomized participants. Participants will be grouped according to their planned treatment. Exploratory endpoints will be analyzed in the ITT Population.

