6.15 Exploratory Analyses

Exploratory analyses will be performed in the ITT population.

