6.15.1 Revised Amyotrophic Lateral Sclerosis Functional Rating Scale (ALSFRS-R)

ALSFRS-R will be measured at Screening, Day 0 pre-dose, Day 30, Day 60 pre-dose, Day 84, Day 120 pre-dose, Day 144 and Day 180.

QMD Ref: Worldwide-TMP-ST-005-7.0 Effective: 12Aug2019	Governing QMD: Worldwide-SOP-ST-001
Confidentiality Statement	

This document is the property of Worldwide Clinical Trials Inc. and may not be duplicated, copied, altered or removed from company without prior approval from Worldwide Quality Assurance or in compliance with Worldwide Standard Operating Procedures.

Worldwide Clinical Trials Controlled Quality Management Document		
 WORLDWIDE CLINICAL TRIALS	Sponsor:	Helixmith Co., Ltd.
	Protocol Number:	VMALS-002-2
STATISTICAL ANALYSIS PLAN VERSION 3.0		

Total score and subscores for Fine and Gross Motor Functions and for Bulbar Function and their changes from baseline will be presented with descriptive statistics by visits and treatment group (Table 14.6.1, Listing 16.2.9.1).

Slope of the total score will be provided using graphical presentation of values by visit for both treatment group.

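### SAP 6.2.14 keeps early-termination assessments out of the by-visit exploratory tables, so rows labelled ITT describe only the participants still attending

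*SAP*

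**What the plan says.** SAP 6.2.14 sets the rule in two sentences: "Only scheduled post-baseline values will be tabulated", and then "Post-baseline repeated, unscheduled and early termination assessments will not be included in tables". The excluded values go to listings only.

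Protocol 7.2 makes the ET visit a planned data collection: "The following assessments will be performed at an Early Termination (ET) Visit, if possible, for Participants who discontinue prior to the Day 180 Visit". Its list includes SVC, HHD, ATLIS, ALSFRS-R, ALSAQ-40, PGIC and CGIC, which are the measures summarised in Tables 14.6.1-14.6.7.

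SAP 6.1.2 defines the population: "The Intent to Treat (ITT) Population consists of all randomized participants". It adds: "Exploratory endpoints will be analyzed in the ITT Population". For ALSFRS-R, SAP 6.15.1 says that scores and "their changes from baseline will be presented with descriptive statistics by visits and treatment group". The slope endpoint has no fitted slope: "Slope of the total score will be provided using graphical presentation of values by visit for both treatment group". SAP 6.15.2 to 6.15.6 likewise give descriptive statistics by visit, and SAP 6.3 bases continuous summaries on non-missing observations.

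**The concern.** ALS is progressive, so a participant who leaves at Day 100 would on average score worse at Days 120, 144 and 180. Under the rule that person vanishes from those rows, and the last measurement taken, at the ET visit, appears in no table. The label ITT tells a reader that all randomized participants are represented, but the later rows represent attenders.

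If leaving is related to decline, each arm's later means look better than they should. With 12 Engensis and 6 Placebo participants, a single leaver is a visible share of an arm. The preliminary ALSFRS-R, strength, respiratory and quality-of-life results could then be read more favourably, or compared less reliably, than the collected data warrant.

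**Working it through.** **Does anything in the SAP restore ET values?** The only missing-data rule for an exploratory measure is for ALSAQ-40 (SAP 6.2.11), and it covers unanswered items within a form, not a missed visit. No section maps an ET date to a scheduled visit, imputes a missed visit or fits a model.

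**Inputs from the documents.** Allocation 12:6 (Protocol 5.3). Attrition in the earlier ALS study: 17 of 18 completed 9 months and one died (Protocol 2.2.6.1). The SAP states no dropout rate, SD or power, so there is no plan figure to reproduce. All rates of decline and dropout below are assumptions.

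**Chance that the rule bites.** P(at least one leaver among n) = 1 - (1 - d)^n.

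| d | n = 18 | n = 6 (Placebo) |
|---|---|---|
| 1/18 (earlier study) | 64% | 29% |
| 10% (assumed) | 85% | 47% |
| 20% (assumed) | 98% | 74% |

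**Shift in an arm mean.** With m leavers of n, mean of attenders minus mean of all = (m/n) x (mean of attenders - mean of leavers). If the leaver's Day 180 change is 6 points worse:

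- Placebo: 1/6 = 16.7%, and 1/6 x 6 = 1.0 point.
- Engensis: 1/12 = 8.3%, and 1/12 x 6 = 0.5 point.

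If exactly one of the 18 leaves and everyone is equally likely to be the one, the difference (Engensis minus Placebo) moves by -1.0 with probability 6/18 or +0.5 with probability 12/18. The average is 6/18 x (-1.0) + 12/18 x 0.5 = 0. So there is no systematic bias when dropout is the same in both arms, although a single trial still shows a shift.

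**A worked Placebo arm (assumed).** Four participants lose 1 point a month. Two lose 2 points a month and leave with an ET visit at Day 100. At 30.4375 days a month, Days 100, 120 and 180 are 3.285, 3.943 and 5.914 months.

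- Day 120, all six: (4 x -3.943 + 2 x -7.885)/6 = -5.26. Scheduled-only: -3.94. With both ET values (2 x -3.285 = -6.57 each) placed at Day 120: (4 x -3.943 + 2 x -6.571)/6 = -4.82.
- Day 180, all six: (4 x -5.914 + 2 x -11.828)/6 = -7.89. Scheduled-only: -5.91. Placing the ET values at Day 120 leaves this row at -5.91, a gap of 1.97 points.
- Slopes at actual dates: each leaver gives -6.571/3.285 = -2.0 a month, so the arm mean is (4 x -1 + 2 x -2)/6 = -1.33 a month, the true value.

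**Simulation (assumed inputs).** 4,000 trials per scenario, 12:6; slope mean -1.0 a month (SD 0.8), residual SD 1.5, leaving time uniform over Days 30 to 175, and log-odds of leaving linear in the participant's own slope. Entries are Day 180 change: Placebo mean / Engensis minus Placebo.

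| Scenario (Placebo / Engensis dropout) | All randomized | Scheduled-only | ET value put in Day 180 row |
|---|---|---|---|
| No effect, dropout unrelated to slope (15% / 15%) | -5.96 / 0.04 | -5.98 / 0.06 | -5.55 / 0.02 |
| No effect, slope-related (15% / 15%) | -5.94 / 0.01 | -5.22 / 0.01 | -5.30 / 0.00 |
| Effect 0.5 a month, slope-related (15% / 8%) | -5.94 / 2.95 | -5.23 / 2.67 | -5.30 / 2.59 |
| Effect 0.5 a month, strongly slope-related (16% / 7%) | -5.93 / 2.96 | -4.80 / 2.33 | -5.12 / 2.42 |

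Per-participant slopes from all visits plus the ET value averaged -0.99 to -1.01 a month in Placebo in all four scenarios. Where the true effect was 0.5, their difference was 0.50. Slopes without the ET value were not computed, so the ET value's own contribution is not isolated.

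**The case against.** The strongest case is that little hangs on this. The endpoints are exploratory and carry no test. Scheduled visits before withdrawal stay in the tables. Participants who stop study drug but agree to stay are still followed (Protocol 7.1). SAP 6.3 shows the number of observations in each summary, SAP 6.4 tabulates withdrawals by reason, and every ET value is listed, which is reviewable with 18 people. ITT in SAP 6.1.2 also says who is included and how they are grouped; it is not a missing-data rule. All of this stands and limits the weight of the point. None of it puts the ET values into a summary.

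Four stronger readings are tempting, and the documents do not support them.

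- That leavers are known to be the fastest decliners. No section says so. The single loss in the earlier study was a death, which may yield no ET visit. At 1/18, two or more leavers among six Placebo participants has probability of about 4%, so the worked example above is an unlikely case at that rate.
- That the comparison of arms is necessarily biased. With equal slope-related dropout, the simulated difference was 0.01 under the rule and 0.01 for all randomized.
- That ET values are barred from the figures. SAP 6.2.14 names tables only. SAP 6.15.1 plots values by visit and is silent on ET.
- That moving each ET value to the nearest empty visit cures the problem. It leaves Day 180 unchanged in the worked example. ALSAQ-40, PGIC and CGIC have only Days 84 and 180 after baseline, so a Day 100 value could be shown as Day 180, 80 days early. In the first simulated scenario, filling Day 180 this way created a bias that scheduled-only means did not have.

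One might also argue that, because the protocol pairs the visits as Day 180/ET, an ET value would be tabulated as Day 180. The explicit wording of SAP 6.2.14 rules that out.

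**Conclusion.** The point holds in limited form. A stated rule discards planned measurements from every exploratory table, and by-visit rows labelled ITT describe attenders only. Whether arm means are then too favourable rests on the assumption that faster decliners leave more often. On that assumption, one Placebo leaver whose Day 180 change is 6 points worse shifts the displayed mean by 1.0 point, and one Engensis leaver by 0.5. The difference between arms is biased only when dropout differs by arm. In the two simulated cases of that kind, a true 2.95 became 2.67 and a true 2.96 became 2.33, which understates the effect; more loss of fast decliners from Engensis would push the other way.

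The slope result assumes a roughly linear decline. Protocol 2.1 reports a plateau or slowing up to Day 90 in the earlier study, so an early leaver's slope may not represent the later course. No test and no primary safety conclusion changes. This is a worthwhile improvement that uses data already planned.

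**What to change.** Amend SAP 6.2.14, with matching text in 6.15, before database lock:

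1. For the ALSFRS-R slope endpoint, compute a slope for each participant from all assessments, including ET, at their actual dates, and summarise it by arm. State how many participants have no post-baseline assessment and hence no slope. In Figures 14.4.1.3-14.4.1.5, plot ET values at their actual dates.
2. In Tables 14.6.1-14.6.7, admit an ET value only when it falls within a pre-stated maximum window of a scheduled visit that has no value. Keep the scheduled-only table alongside. Do not carry an ET value to a distant Day 180 row; this matters most for ALSAQ-40, PGIC and CGIC.
3. Show the number of ET values per visit and arm.

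The cost is SAP wording, a visit-mapping rule and a second version of the affected tables; no new data are collected. The downside is that a tabulated ET value may lie some days from its nominal visit, up to the window limit. A narrow window would leave some ET values, such as one 20 days before Day 120, in the slope and figure only. Tabulating ET values by visit reduces the bias but does not remove it at Day 180, and nothing here helps for deaths without an ET visit.
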